Inclusion criteria. Participants must be pregnant women ≤ 13 week-gestation with a single fetus as assessed by ultrasound (Research staff or [name], Co-I, a board-certified Ob/Gyn at a collaborating clinic will verify eligibility from the patient's Electronic Health Record, EHR). Participants must also have self-reported (1) pre-pregnancy body mass index (BMI) of 25.0-45.0 kg/m² and height (we will use height and weight to compute body mass index). (2) ability to read and speak English, (3) age of 18-45 years, (4) access to a working smart phone with unlimited text messaging (89 to 94% of American adults aged 18 to 49 years own a smart phone)⁹⁷ and access to internet and (5) receipt of prenatal care and from our collaborating clinics and plan to deliver the baby at The Ohio State University (OSU) Wexner Medical Center, 6) a resident of Franklin Count, and (7) committed to the 20-week intervention.

Exclusion criteria. Self-reported (1) history of ≥ 3 miscarriages, (2) planned termination of the pregnancy, (3) diagnosed hypertension and type 1 or 2 diabetes, (4) history of or current diagnosis of an eating disorder, (5) serious current physical disease (e.g., renal disease or cancer), (6) past bariatric surgery, (7) current or history of substance abuse in the past 6 months, (8) current treatment for a serious psychological disorder (e.g., schizophrenia and bipolar disorder) or (9) contraindications to walking. Consented women will become not eligible to participate in the study if they are not randomized by 16-week 6 days gestation (see D. Detailed Study Procedure: Recruitment and enrollment)—this is because the study intervention starts ≤ 17 weeks gestation. Also, women will become not ineligible for participation if they did not complete the baseline data (T1): online survey via REDCap, two 24-hour dietary recall and wear the Actigraph monitor for at least 4 consecutive days with 6 hours per day.

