Sample size/power. Our primary outcome variable is weekly gestational weight gain (GWG). A final sample size of 72 women (36 per group, after accounting for 20% attrition from the 90 enrolled) will have 80% power to detect a time-averaged between-group difference in weekly GWG with a medium effect size (standardized between-group difference of 0.6). This effect size is translated to a between-group difference of 0.33 lb in weekly GWG, assuming a common standard deviation of 0.55 lb (or 0.25 kg) based on previous research.²⁷ The power analysis was conducted using mixed-effect linear modeling with a two-sided significance level of 0.05, assuming a correlation of 0.7 between the two weekly GWG measures. Due to the pilot nature of the study, our sample size is not powered to detect smaller effect sizes (<0.6). Nevertheless, we will report point estimates, effect sizes, and 95% confidence intervals. These estimates along with clinical significance will guide the results interpretation and sample size determination for a future full-scale RCT (R01).

C. Measurement/ Instrumentation

All participants will be assessed at ≤ 16 week-gestation (T1), 24-27 week-gestation (T2) and 35-37 week-gestation (T3). Survey data will be collected online using password-protected security-ensured Research Electronic Data Capture (REDCap), a secure web application for building and managing online surveys and databases. Primary and secondary outcomes will be extracted from electronic health record. An incentive of \$40 will be provided for participation in each point of data collection for all measurements.

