Lifestyle behaviors. Dietary intake will be assessed using the NCI Automated Self-Administered 24-hour recall (ASA24). Participants will complete 24-hour recalls on two random days over a week.^{99,100} The variables of interest include calories, fat, sugary drinks, fruit and vegetable intakes. Physical activity will be assessed using Actigraph (GT3x), an objective measurement of walking steps and energy expenditure. We will distribute the Actigraph in person (T1, C.3.2) and mail it to participants' home (T2 and T3) to wear at the waist for \geq five consecutive days (\geq 10 hours/per day) except showers/baths and water activities. Then, they will return the Actigraph with steps recorded when we measure their weight at T1, T2 and T3. Psychological eating. We will use the Modified Three-Factor Eating Survey (18 items) to assess emotional eating (3 items), overeating (9 items) and restrained eating (6 items)¹⁰¹ to measure psychological eating. *Eating out of boredom*. We will use the modified emotional eating scale (8 items).¹⁰²

Concepts. Motivation. *Autonomous motivation* will be measured using Treatment Self-Regulation Questionnaire (18 items) that asks why the respondent does a behavior.¹⁰³ Self-efficacy will be measured using a 10-item survey for coping self-efficacy,¹⁰⁴ an 8-item survey for healthy eating self-efficacy,¹⁰⁵ and a 10-item survey for physical activity self-efficacy¹⁰⁴ that ask participants' confidence in performing the specific activity. Consideration of future will be measured using consideration of future consequences 14 scale (14 items: 7 items measuring future consequences and 7 items measuring immediate consequences).¹⁰⁶ Happiness will be measured using the subjective happiness survey (4 items).¹⁰⁷ Hope will be measured using Snyder Hope Survey (12 items).¹⁰⁸ Prenatal anxiety will be measured using the revised prenatal distress questionnaire (17 items).¹⁰⁹ Food insecurity will be measured using USDA Food Insecurity Survey (18 items).¹¹⁰

Emotion. Emotion control will be measured using the Emotion Regulation Questionnaire (10 items) that assess emotion regulatory process using reappraisal, suppression and regulating negative emotion.¹¹¹ Stress will be measured using The Perceived Stress Scale (10 items)¹¹² that measures the degree to which situations in one's life are appraised as stressful. Depressive symptoms will be measured using the 10-item Edinburgh Postnatal Depression Scale¹¹³

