Cognition. Executive function will be measured using The Behavior Rating Inventory of Executive Function- Adults (BRIEF-A, 75 items).¹¹⁴ This survey measures an adult's executive function in her everyday environment: for example, inhibitory control, self-monitoring, plan/organization, and organization of materials. BRIEF-A has been used in prior RCTs and is sensitive to detect changes in executive function over time.¹¹⁵⁻¹¹⁷ Impulsiveness will be measured using Barratt Impulsiveness Scale (30 items).¹¹⁸

Process evaluation. All participants will report receipt of lifestyle behavior counseling from their clinicians, midwives and dietitians and joining other programs.

Sent messages to participants

We will email and text participants to complete study activates. Please note the sequence listed below corresponding to the sequence listed on the file called "All Email and Text Messages."

| Activities | Email | Text | Notes |
|--|-------|------|---------------|
| #1 Attend information session (first zoom meeting) | Yes | Yes | Up to 3 times |
| #2 Consent to full participation (Consent and HIPAA Authorization) | Yes | NO | One time |
| #2-A. REDCap for electronic signature | Yes | Yes | One time |
| #3. Delivery and pick up Actigraph | Yes | Yes | Up to 3 times |
| #4 Attend second zoom meeting | Yes | Yes | Up to 3 times |

| Intervention Phase | | | |
|--|--|-----|---|
| 1A: Complete Part I intervention: becoming a better me | | Yes | Yes |
| | | | Need to send both email and text (at the same time) because of including web link—participants can complete via smart phone or computer internet access. Up to 3 times for each |
| 2A. Complete Part II intervention: safe care booster | | Yes | Yes |
| | | | Need to send both email and text (at the same time) because of including web link. Up to 3 times |
| 3A. Join the individual coaching via zoom | | Yes | Yes |
| Throughout the project | | | |
| 1A. 24-hour dietary recall | | Yes | Yes |
| | | | Need to send both email and text (at the same time) because of including web link. Up to 6 times (3 times/dietary recall) |
| 2A. Wear Actigraph | | No | Yes |
| | | | Up to 7 times (1/day) when participants wear the Actigraph |
| 3A. Fill out online survey | | Yes | Yes |
| | | | Need to send both email and text (at the same time) because of including web link. Up to 3 times |
| 4A. Cohort retention | | Yes | Yes |
| 5A. Notify Incentives in Email | | No | Yes |
| | | | Up to 3 times |

D. Detailed study procedures

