Usual care. All study participants will receive usual prenatal care from their obstetrician or midwife. The usual prenatal care visit occurs monthly until 28 week-gestation, every other week from 28-36 week-gestation and weekly from 36-week until delivery. At our collaborating clinics, pregnant women are weighed at each prenatal visit and will receive additional healthy eating counseling, e.g., if they have GDM. To improve retention of women randomly assigned to the usual care group, we will email study newsletters every other month with general information about pregnancy-related health (e.g., over-the-counter medication).

Intervention: A self-directed, web-based GOEFT lifestyle behavior intervention (tailored to participants' needs). ***Intervention mode.*** Intervention participants will receive all aspects of usual care plus a self-directed, web-based GOEFT lifestyle behavior intervention. Previous self-directed, web-based interventions have effectively promoted weight management in overweight or obese adults.¹²³⁻¹²⁵ Also, EFT has been delivered on the web and shown promise for promoting weight management.^{63,126} ***Intervention duration, dosage and topics.*** The intervention will last 20 weeks (start \leq 17 weeks gestation), a duration effectively preventing EGWG in overweight or obese women.²⁰⁻²⁸ Intervention participants will complete weekly online activities (35-40 min/week) via their smart phone or internet access from any location. The intervention includes *three topics*: stress management, healthy eating, and PA (Figure 2). ***Intervention (long-term) goals.*** Participants are strongly encouraged to (1) daily manage stress and emotional reactions using positive strategies, (2) daily eat a diet low in fat and consume less sugary drinks, (3) daily eat a diet high in fruits and vegetables, and (4) walk at a brisk pace for 30 min most days a week.¹²⁷

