
Intervention implementation (Figure 3). After randomization and while intervention participants are still at the central study clinic (Visit 2), the Project Director will be present and provide the intervention web link and instructions on completing the weekly intervention activities online. Intervention participants will then use their smart phone, first and last name, and birthday to log into the website to complete the Part I intervention activities for week one. The day of the week that the participants complete the Part I intervention activities at WIC/HS will count as their weekly day one. The Project Director will answer questions and provide technical support as needed. S/he will observe and record the extent to which participants need assistance from the study office to complete the EFT intervention activity throughout the 20-week intervention. Participants who need substantial assistance will provide the best time to call so a research assistant can help them complete the intervention activities (e.g., read the responses to them over the phone). All participants will be given the study office number to call for questions and technical problems. Participants will use their own device to complete Part II intervention activities for week one and the additional 19 weeks of the intervention at convenient times and locations. We will send the web link to participants weekly via email and text with an “intervention adherence” text message reminder (generated by the participants) to log in and complete the intervention activities. We will lend hotspot connections to intervention participants who lose their internet connection and are unable to access the intervention website outside their home.

| |
|--|
| Figure 3. GOEFT: A 20-week self-directed, web-based intervention (35-40 min/week) |
| Part 1 (Weekly Days 1-4: 30-35 min) |
| Motivation (AuM, SE) |
| -Three most important personal values, ways to commit to personal values followed by ways to boost confidence in achieving personal values |
| Emotion (EC, Stress) and Cognition (ExF) |
| -The first short-term goal, WHAT (the week's goal), WHY (importance of the goal), WHEN and WHERE (the goal taking place), WHO (persons involved in the goal) and HOW (generating three steps to achieve the goal) followed by selecting the second short-term goal and repeating five Ws and H |
| Motivation (SE) |

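### Hotspots are lent only to intervention women, although the T2 and T3 surveys and dietary recalls are online in both arms; this could cause arm-dependent missing data in the online measures of Aims 3 and 4

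*Combined protocol and SAP*

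**What the plan says.** Section D, under Intervention implementation (Figure 3), makes a loan available to one arm: "We will lend hotspot connections to intervention participants who lose their internet connection and are unable to access the intervention website outside their home". The offer is tied to reaching the intervention website. No equivalent for usual care appears elsewhere.

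Outcome collection is the same in both arms. Section C, Measurement/Instrumentation, sets the schedule: "All participants will be assessed at ≤ 16 week-gestation (T1), 24-27 week-gestation (T2) and 35-37 week-gestation (T3". It also sets the survey mode: "Survey data will be collected online using password-protected security-ensured Research Electronic Data Capture (REDCap". Under Lifestyle behaviors: "Dietary intake will be assessed using the NCI Automated Self-Administered 24-hour recall (ASA24". The table of messages in section C lists the recall and the online survey among activities running throughout the project and sends both as links; for the recall it notes "Need to send both email and text (at the same time) because of including web link. Up to 6 times (3 times/dietary recall".

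The retention measure specific to usual care is in section D, Usual care: "To improve retention of women randomly assigned to the usual care group, we will email study newsletters every other month". Cohort retention, also in section D, adds measures not limited to one arm: a monthly call, tolerance of partial data collection, longer collection windows, and logs of reasons for dropout.

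**The concern.** The hotspot is written as an aid to delivering the intervention, but a working connection also lets a woman open the survey and recall links. Whether a woman who loses internet gets help that would let her return outcome data therefore depends on her arm.

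Women who lose internet may be under more financial strain and stress, which bears on diet and on the Aim 4 scales. If they stay observable in one arm more than in the other, the arms are compared on differently selected women at T2 and T3. The formal retention criterion in section F (Aim 1) would not show this: it counts measured body weight at T3, so a woman can meet it with no follow-up survey at all.

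**Working it through.** **1. Which outcomes need the woman's own internet access**

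| Outcome | Source | Needs her internet? |
|---|---|---|
| Weekly weight gain; maternal and birth outcomes | Health record | No |
| Steps, energy expenditure (Aim 3) | Actigraph, mailed at T2 and T3; described as "an objective measurement of walking steps and energy expenditure" | No |
| Calories, fat, sugary drinks, fruit and vegetables (Aim 3) | ASA24 by link | Yes |
| Psychological eating (Aim 3) | Online survey | Yes |
| Motivation, emotion, cognition (Aim 4) | Online survey | Yes |

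The point is confined to the last three rows.

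**2. The plan's own figures**

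The only power figure concerns weekly weight gain (section B, Sample size/power): difference 0.33 lb, SD 0.55 lb, correlation 0.7 between two measures, 36 per group, two-sided 0.05.

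- Attrition: 90 × (1 − 0.20) = 72, or 36 per group.
- SD of the mean of two measures: 0.55 × √((1 + 0.7)/2) = 0.507.
- Standard error: 0.507 × √(2/36) = 0.1195.
- Power: Φ(0.33/0.1195 − 1.96) = Φ(0.80) = 78.8% by the normal approximation (77.7% by noncentral t), against 80% stated.

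The figure reproduces to within about two points, and this point does not touch it. The plan gives no power for Aims 3 and 4 and no rate of internet loss.

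**3. Size, under stated assumptions**

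Let a share q of the 36 usual care women lose access and give no online follow-up, and let them differ from the rest by d SD. If the rest have mean m, the full mean is (1 − q)m + q(m − d) = m − qd, so the complete-case mean is off by qd. The standard error of a single-time standardized difference is √(1/36 + 1/(36(1 − q))).

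| q (assumed) | Women lost (36q) | Shift, d = 0.25 | d = 0.5 | d = 1.0 | SE |
|---|---|---|---|---|---|
| 2% | 0.7 | 0.005 | 0.010 | 0.020 | 0.237 |
| 5% | 1.8 | 0.013 | 0.025 | 0.050 | 0.239 |
| 10% | 3.6 | 0.025 | 0.050 | 0.100 | 0.242 |
| 15% | 5.4 | 0.038 | 0.075 | 0.150 | 0.246 |
| 20% | 7.2 | 0.050 | 0.100 | 0.200 | 0.250 |

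At q = 5-15% and d = 0.5 the shift is 0.025-0.075 SD; 0.075/0.246 = 0.30 of a standard error. Across the whole grid it stays below one standard error (at most 0.200/0.250 = 0.8).

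The 36 is already net of 20% attrition, and the documents do not say whether loss of access belongs to that 20%. The counts are therefore rough; the shift qd does not depend on the base.

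**4. Recovery from baseline**

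Completion of the T1 measures is a condition of eligibility (section B), and effects for Aims 3 and 4 are compared as change from baseline (section F). If the correlation between T1 and follow-up is 0.5-0.8 (assumed) and the 0.5 SD gap is already present at T1, the unrecovered part is 0.5 × (1 − 0.8) = 0.10 to 0.5 × (1 − 0.5) = 0.25 SD per lost woman. The residual shift is then 0.05 × 0.10 = 0.005 to 0.15 × 0.25 = 0.0375 SD.

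**The case against.** The strongest reply is that losing internet is not the same as losing data.

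- Every woman must have "access to a working smart phone with unlimited text messaging" and internet access at entry. Usual care women need a connection for only two follow-up assessments, each with a window of weeks that may be extended.
- The monthly call reaches both arms by telephone, and staff ask what adjustments could keep a woman in the study.
- Section F goes beyond the mixed model: it plans to examine missingness patterns, use multiple imputation, fit pattern-mixture models if data are not missing at random, and run sensitivity analyses.

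Much of this stands, and it lowers the risk. It does not close the gap. The entry criterion says nothing about access later, and the plan itself foresees that some intervention women will lose it although they too have smartphones. The criterion specifies unlimited texting; it does not specify unlimited data. A call can discover an access problem, but the plan gives staff no loan for a usual care woman. The telephone help it describes is for intervention activities. A longer window helps only if access returns. Whether data are missing not at random cannot be established from the observed data, so that trigger for pattern-mixture modeling is weak.

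A reader might infer that usual care women are selectively removed from Aims 3 and 4 and that the effect is therefore understated. The documents do not support that. Actigraph outcomes are outside the problem, and T1 data remain in the model. Nothing shows that a lent hotspot keeps intervention women answering surveys; the documents do not say whether it may be used for data collection. The intervention arm also carries 35-40 minutes of weekly activity and ten coaching calls, which could cause dropout in the other direction.

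**Conclusion.** The asymmetry is real on the face of the text: access support is offered by arm, while the online T2 and T3 measures need access in both. It could cause arm-dependent missing data in diet, psychological eating, motivation, emotion and cognition. The primary outcome and every other outcome taken from the health record or the Actigraph are untouched.

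The expected size is small. The illustrative 0.025-0.075 SD rests on an assumed 5-15% loss and an assumed 0.5 SD difference, neither of which has a source in the documents, and it is before recovery from baseline. Bias further requires that women who lose access differ in ways their earlier responses and the covariates do not explain. The net direction is uncertain. The case for acting rests on a cheap, avoidable asymmetry, not on a demonstrated large bias.

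**What to change.** Change the sentence in Intervention implementation so that a hotspot loan is offered to any randomized woman, in either arm, who loses internet. For usual care, limit the loan to the T2 and T3 survey and dietary-recall windows, which leaves the intervention contrast intact. Record loans, and completion of the online measures, by arm. These records would also inform the feasibility aim and the planned full-scale trial.

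The cost is one protocol sentence and a few short loans of devices the study already plans to lend. The downside is data and mailing cost for a handful of usual care women.
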